## **9. STUDY DRUG**

The term "study drug" will be used to refer GDC-0810.

### **9.1 GDC-0810**

#### **9.1.1 Description and Composition of the Drug Substance**

Chemical Name: (2S,3R,4R,5R)-2,3,4,5,6-pentahydroxy-N-methylhexan-1-aminium (E)-3-(4-((E)-2-(2-chloro-4-fluorophenyl)-1-(1H-indazol-5-yl)but-1-en-1-yl)phenyl)acrylate

Code Name: GDC-0810 N-Methyl-D-Glucamine (NMG) Salt

Molecular Formula: C33H37CIFN3O7 (C26H20CIFN2O2 • C7H17NO5)

Molecular Weight: 642.11 Daltons (neutral form 446.90 Daltons)

Appearance: White to yellow to tan crystalline solid

#### **9.1.2 Study Drug Product**

GDC-0810 will be provided in two different strengths: 50 mg (8 mm white round tablet containing 50 mg GDC-0810 free acid) and 200 mg (19 mm×8 mm white caplet containing 200 mg GDC-0810 free acid). Inactive ingredients include microcrystalline cellulose (Avicel PH101), sodium laurel sulfate, sodium bicarbonate, sodium carboxymethylcellulose (Croscarmellose Sodium), fumed silica (Cab-O-Sil), and magnesium stearate.

#### **9.1.3 Packaging and Labeling**

GDC-0810 will be supplied as 50 or 200 mg tablets (depending on total dose levels) packaged in 30-ct, 100 cc HDPE bottles with child-resistant closures and tamper-proof heat induction seals.

Each bottle of study drug will be labeled with the required regulatory agency warning statement, lot number, the Sponsor's name, and directions for patient use and storage.

## **10. STUDY TREATMENTS**

The term "study treatment" will be used to refer to palbociclib and/or LHRH agonist.

### **Palbociclib (Cohorts C0 and C1)**

Refer to palbociclib package insert for details on the formulation and storage of palbociclib. Palbociclib will be *supplied* by the Sponsor. The Sponsor does not intend to provide other study interventions to patients after the conclusion of the study or any earlier withdrawal.

### **Luteinizing Hormone Releasing Hormone Agonist (LHRH) (Cohort D1)**

Choice of LHRH agonist will be an institutional choice approved for use in breast cancer. Refer to LHRH agonist package insert for details on the formulation and storage of LHRH agonist. If patient becomes intolerant to current LHRH agonist, then patient may switch to another approved LHRH agonist during trial. LHRH agonists will be prescribed by the study sites and cost of study treatment will be reimbursed by the Sponsor for the duration of the study. The Sponsor does not intend to provide other study interventions to patients after the conclusion of the study or any earlier withdrawal.

#### **10.1 TREATMENT DOSE ASSIGNMENT**

##### **10.1.1 Phase Ia**

Standard 3+3 design will be followed for dose-escalation in Phase Ia. The starting dose in Phase Ia of GDC-0810 single agent (Cohorts 1–9) will be 100 mg per day, followed by dose escalation to 200 mg (dose level 2), and by 200 mg increments thereafter ([Table 3](#)).

In Phase Ia, a minimum of 3 evaluable patients will be entered at each dose level. If 1 out of the first 3 patients enrolled at any given dose level experiences a DLT, 3 additional patients will be assigned to that dose level. If  $\leq 1$  patient in 6 experiences a DLT, dose escalation will proceed.

In Phase Ia if  $\geq 2$  patients at any given dose level experience a DLT, dose escalation will stop and the MTD may be defined as either the previous dose level or upon further evaluation of an intermediate lower dose level (e.g., by 100 mg decrement).

If no DLTs are observed, the RP2D will be based on the overall safety and PK/PD profile of GDC-0810 single agent (Phase Ia), and not necessarily the MTD. The decision to dose escalate or dose reduce will be made during dose escalation data review teleconferences held between the Sponsor and the investigators.

If only 3 patients have been treated at a dose level under consideration as the MTD and/or RP2D, a minimum of 3 additional patients will be treated at that dose level to confirm the MTD and/or RP2D.

In Phase Ia, dose escalation will continue until either of the following has been observed:

The MTD has been exceeded (incidence of DLT  $\geq 33\%$ ); or

Pharmacokinetic futility (defined as a lack of increase in exposure with increasing doses of GDC-0810 in at least two successive dose levels) is encountered.

Patients enrolled in Phase Ia will continue treatment at their assigned dose level for at least 2 cycles and observed for cumulative toxicity. After 2 cycles, they may then be treated at the next higher dose level provided it has been shown to be safe (passed the DLT evaluation period) in a previously treated cohort at the discretion of the investigator and in agreement with the patient.

**Table 3 Dose Levels for Escalation for Phase Ia (Cohorts 1–9)**

Dose Level	GDC-0810
1	100 mg
2	200 mg
3	400 mg a
4+	By 200 mg increments from the previous dose

a Starting dose of GDC-0810 in Cohort C1 in Phase Ib.

### **10.1.2 Phase IIa**

In the Phase IIa dose-expansion portion of Study GO29642 patients will receive the RP2D of 600 mg QD administered within 30 minutes after a meal.

### **10.1.3 Phase Ib**

#### **10.1.3.1 Cohort C1**

*GO29642 study enrollment in Phase Ib has been discontinued. No patients will be enrolled in Phase Ib Cohorts C2 and C3.*

Standard 3+3 design will be followed for dose-escalation in Cohort C1 of the Phase Ib study.

The starting dose for Phase Ib Cohort C1 dose escalation of GDC-0810 will be 400 mg per day on Days 1–28 of a 28-day schedule, taken together with 125 mg palbociclib administered on Days 1–21 of a 28-day schedule (21/7) ([Table 2](#)).

In Cohort C1 of Phase Ib, a minimum of 3 evaluable patients will be entered at each dose level. If 1 out of the first 3 patients enrolled at any given dose level experiences a DLT, 3 additional patients will be assigned to that dose level. If  $\leq 1$  patient in 6 experiences a DLT, dose escalation will proceed. If dose level C1 is deemed intolerable in the absence of DLTs, de-escalation to dose level C0 may occur.

In Cohort C1 of Phase Ib, if  $\geq 2$  patients at any given dose level experience a DLT, dose escalation will stop and the MTD may be defined as either the previous dose level or upon further evaluation of an intermediate lower dose level.

In addition to any DLTs, other available relevant demographic, adverse event, laboratory, dose administration, PK, and PD data will be reviewed prior to all dose escalation decisions.

If no DLTs are observed, the RP2D will be based on the overall safety and PK/PD profile of GDC-0810 and palbociclib, and not necessarily the MTD. The decision to escalate or reduce the dose will be made during dose-escalation data review teleconferences held between the Sponsor and the investigators.

If only 3 patients have been treated at a dose level under consideration as the MTD and/or RP2D, a minimum of 3 additional patients will be treated at that dose level to confirm the MTD and/or RP2D.

Patients enrolled in Cohort C1 of Phase Ib will continue treatment at their assigned dose level for at least 2 cycles and observed for cumulative toxicity. After 2 cycles, they may then be treated at the next higher dose level provided it has been shown to be safe (passed the DLT evaluation period) in a previously treated cohort at the discretion of the investigator and in agreement with the patient.

#### **10.1.3.2 Cohort D1**

*Study GO29642 enrollment in Phase Ib has been discontinued. No patient will be enrolled in Cohort D2.*

Cohort D1 of the Phase Ib study is a safety run-in of 6 patients.

The dose of GDC-0810 in Phase Ib Cohort D1 safety run-in will be 600 mg per day. Dose escalation is not planned for either drug in Cohort D1. However, the dose of GDC-0810 in Cohort D2 may be reduced on the basis of joint review by Sponsor and study investigators of available safety and tolerability data.

In Phase Ib Cohort D1, if 2 or more patients at the combination dose level experience a DLT, evaluation of a lower dose level of GDC-0810 may be initiated.

In addition to any DLTs, other available relevant demographic, adverse event, laboratory, dose administration, PK, and PD data will be reviewed.

If no DLTs are observed, the RP2D will be based on the overall safety and PK/PD profile of and LHRH agonist and not necessarily the MTD. The decision to reduce the dose of GDC-0810 will be made during data review teleconferences held between the Sponsor and the investigators.

## **10.2 DLT DEFINITION**

For DLT evaluation, toxicity will be graded according to the National Cancer Institute Common Toxicity Criteria for Adverse Events (NCI CTCAE; Version 4.0) ([Appendix 7](#)).

### **10.2.1 Phase Ia**

For Phase Ia, the DLT evaluation period will start from the first dose of GDC-0810 (Day -7) through the first cycle (28 days) of treatment for a total of 35 days.

For Phase Ia, patients who miss 7 or more doses of GDC-0810 during the DLT evaluation period due to reasons other than a DLT will be replaced.

In addition, patients who are discontinued from the study prior to completing the DLT evaluation period, due to reasons other than a DLT (e.g., disease progression, consent withdrawn), will also be replaced.

#### **DLT Definitions**

For Phase Ia, DLTs will be defined as any of the following adverse events that are deemed by the investigator or the Sponsor to be related to study drug (toxicities will be attributed to single agent GDC-0810 unless they are clearly related to disease progression or can clearly be attributed to a cause other than GDC-0810 administration):

- Any grade  $\geq 3$  non-hematologic toxicity (excluding alopecia)
- Any grade  $\geq 3$  hematologic toxicity of  $> 7$  days' duration
- Any grade toxicity that leads to study drug interruption of  $> 7$  days' duration

### **10.2.2 Phase IIa**

DLT definitions are not applicable for the Phase IIa dose expansion portion of the study.

### **10.2.3 Phase Ib**

*No patients will be enrolled in Phase Ib Cohorts C0 and C2.*

For Phase Ib Cohorts C0, C1, and D1, the DLT evaluation period will start from Day 1 through Day 28 of Cycle 1.

For Phase Ib, patients who miss  $\geq 7$  doses of GDC-0810 or  $\geq 5$  doses of palbociclib (in Cohort C0 or C1) during the DLT evaluation period due to reasons other than a DLT will be replaced.

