## 2.2 CLINICAL OVERVIEW OF PALBOCICLIB

Palbociclib is being evaluated in many cancer types including breast, ovarian, gastrointestinal stromal tumors (GIST), liposarcomas, acute leukemias, and mantle cell lymphomas.

The DLT of palbociclib is reversible myelosuppression, specifically reversible neutropenia (Gr 1–2: 33–54%; Gr 3–4: 20–50%). Other hematological toxicities include thrombocytopenia (Gr 1–2: 7–58%; Gr 3–4: 0–17%) and anemia (Gr 1–2: 20–64%; Gr 3–4: 2–17%). Phase I and II clinical trials demonstrate that palbociclib is a well-tolerated agent with mild to moderate fatigue (10–34%), nausea (24–30%), and diarrhea (1–30%) as the most commonly reported non-hematological adverse reactions (Schwartz et al. 2011; Flaherty et al. 2012; Dickson et al. 2013; Vaughn et al. 2015). Grade 3 and Grade 4 febrile neutropenia occurred in one of 30 patients (3%) in the two single-agent Phase II studies, respectively (Dickson et al. 2013; Vaughn et al. 2015).

The PALOMA-1 Phase II study randomized women with advanced ER+ human epidermal growth factor 2 (HER2-) breast cancer who had not received any systemic

treatment for their advanced disease to receive either letrozole 2.5 mg QD alone or with palbociclib 125 mg QD administered daily for 21 days followed by a seven day off-period (21/7). The most common adverse events reported for the palbociclib plus letrozole group were neutropenia (74%), leukopenia (43%), fatigue (40%), anemia (35%), and nausea (25%). Grade 3 treatment-related adverse events (AEs) reported in  $\geq 20\%$  of patients were neutropenia (48%) and leukopenia (19%). There were no cases of febrile neutropenia reported. The most frequently reported Grade 4 adverse events were neutropenia (6%), pulmonary embolism (5%), and fatigue (2%). The results showed substantial efficacy with the palbociclib and letrozole combination by significant improvement in median progression-free survival of 20 months (95% CI: 13.8, 27.5 months) compared to letrozole alone (10.2 months; 95% CI: 5.7, 12.6 months) ([Finn et al. 2009](#)). Palbociclib received accelerated approval from the United States Food and Drug Administration (FDA) in 2015.

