## Phase Ib Cohorts C0 and C1 DLT Definitions

DLT definitions reflect the known and expected toxicities of GDC-0810 administered alone and palbociclib administered alone or in combination with other endocrine therapies. A DLT is defined as one of the following toxicities occurring during the DLT assessment window and considered by the investigator to be related to GDC-0810 or palbociclib.

- Any Grade  $\geq 3$  non-hematologic, non-hepatic toxicity with the exception of:
  - Alopecia of any grade;
  - Grade 3 nausea, vomiting, or diarrhea that resolves to Grade  $\leq 2$  within 24 hours with maximal medical therapy
  - Grade 3 fatigue, unless the fatigue has increased by at least two grades from baseline
- Any grade non-hematologic toxicity that leads to study drug or study drug treatment interruption of  $> 7$  days' duration
- Grade  $\geq 3$  elevation of serum hepatic transaminase (ALT or AST) lasting  $> 7$  days
  - For patients with Grade  $\leq 2$  hepatic transaminase levels at baseline as a result of liver metastases, only a transaminase level  $\geq 10 \times$  ULN lasting for  $> 7$  days will be considered a DLT.
- Grade  $\geq 3$  elevation of serum bilirubin
- Any case of potential drug-induced liver injury that includes an elevated ALT or AST in combination with either an elevated bilirubin or clinical jaundice, as defined by Hy's Law as recommended in the U.S. FDA Guidance "Drug-Induced Liver Injury: Premarketing Clinical Evaluation," July 2009:
  - The finding of an elevated ALT or AST ( $> 3$  times baseline value) in combination, with either an elevated total bilirubin ( $> 2 \times$  ULN) or clinical jaundice in the absence of cholestasis or other causes of hyperbilirubinemia is considered to be an indicator of severe liver injury. Therefore, investigators must report as an adverse event the occurrence of either of the following:
    - Treatment-emergent ALT or AST  $> 3$  times baseline value in combination with clinical jaundice
    - Treatment-emergent ALT or AST  $> 3$  times baseline value in combination with total bilirubin  $> 2 \times$  ULN (of which  $\geq 35\%$  is direct bilirubin)

- Grade 4 febrile neutropenia of any duration
- Grade 4 neutropenia  $\geq 10$  days
- Grade 3 thrombocytopenia associated with clinically significant bleeding
- Grade 4 thrombocytopenia associated with:
  - $\geq 10$  days duration
  - Active bleeding
  - Requirement for platelet transfusion

- Grade 4 anemia

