**Table 6 Dose Modification Guidelines for Hematologic Toxicities**

Toxicity	Palbociclib	GDC-0810
Neutropenia or thrombocytopenia Grade $\leq 2$	No dose modification required.	No dose modification required.
Uncomplicated Grade 3 neutropenia	Withhold palbociclib until recovery to Grade $\leq 2$ ( $\geq 1000/\text{mm}^3$ ). No dose adjustment is required unless recovery of neutrophil count is delayed a,b , in which case reduce by one dose level.	No dose modification required.
Uncomplicated Grade 4 neutropenia (ANC $< 500/\text{mm}^3$ )	Withhold palbociclib until recovery to Grade $\leq 2$ ( $\geq 1000/\text{mm}^3$ ). Resume at next lower dose. Reduce by two dose levels c if neutrophil recovery is delayed a or in case of recurrent Grade 4 event.	No dose modification required.
Grade $\geq 3$ neutropenia associated with infection or fever	Withhold palbociclib until neutrophil count recovery to Grade $\leq 2$ ( $\geq 1000/\text{mm}^3$ ) and afebrile and infection is clinically improving. Resume palbociclib at next lower dose. Reduce by two dose levels c if neutrophil recovery is delayed a . In case of Grade 4 febrile neutropenia, discuss with Medical Monitor prior to resuming palbociclib.	No dose modification required.
Uncomplicated Grade $\geq 3$ thrombocytopenia (platelet count $< 50,000/\text{mm}^3$ )	Withhold palbociclib until recovery to Grade $\leq 2$ ( $\geq 50,000/\text{mm}^3$ ). Resume at next lower dose. Reduce by two dose levels c if platelet count recovery is delayed a or in case of recurrent Grade 4 event.	No dose modification required.

ANC=absolute neutrophil count.

a If recovery of neutrophils to  $\geq 1000/\text{mm}^3$  or platelet count to  $\geq 50,000/\text{mm}^3$  takes  $> 2$  weeks (including dose holding due to toxicity, the scheduled week off treatment, or  $> 7$  days of cycle delay).

b If uncomplicated Grade 3 neutropenia recurs in 2 consecutive cycles, after recovery as per retreatment criteria (ANC  $\geq 1000/\text{mm}^3$  and no fever), treatment may restart at the next lower dose level at investigator's discretion.

c If no further dose reduction is possible (i.e. patient is already receiving 75 mg/day according to the 3/1 schedule), consider changing the schedule to 75 mg/day, 2 weeks on/2 weeks off, or discontinue palbociclib and continue with GDC-0810 alone.

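### In Cohorts C0/C1 some treatment-related palbociclib holds are not DLTs yet still cause replacement, so the DLT-evaluable set depends partly on outcome

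*Combined protocol and SAP*

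**What the plan says.** For Cohorts C0, C1 and D1, Section 10.2.3 states that "the DLT evaluation period will start from Day 1 through Day 28 of Cycle 1". Patients who miss at least 7 GDC-0810 doses, or in C0/C1 at least 5 palbociclib doses, "during the DLT evaluation period due to reasons other than a DLT will be replaced". Section 10.4.2 repeats this for C1.

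The C0/C1 DLT list includes "Any grade non-hematologic toxicity that leads to study drug or study drug treatment interruption of" more than 7 days. Its neutropenia items are "Grade 4 febrile neutropenia of any duration" and Grade 4 neutropenia lasting 10 days or more. Asymptomatic Grade 3 laboratory abnormalities that the investigator judges not clinically significant are excluded.

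For both Grade 3 and Grade 4 neutropenia, Table 6 gives the guidance "Withhold palbociclib until recovery to Grade" 2 or better. Section 2.2 says: "The DLT of palbociclib is reversible myelosuppression, specifically reversible neutropenia".

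In Phase Ia (Section 10.2.1), "patients who miss 7 or more doses of GDC-0810 during the DLT evaluation period due to reasons other than a DLT will be replaced". The matching DLT there is "Any grade toxicity that leads to study drug interruption of" more than 7 days, with no restriction to non-hematologic events.

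Section 10.1.3.1 runs the 3+3 rule on evaluable patients, a term defined only through the replacement rule. Section 15.2.3 applies Table 11 to Phase Ib.

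**The concern.** Replacement is meant to remove patients who are uninformative about toxicity. Here the test is whether the missed doses were due to a DLT, not whether they were unrelated to treatment. The missed-dose thresholds (5 palbociclib doses, 7 GDC-0810 doses) also do not meet the interruption-DLT threshold (more than 7 days, non-hematologic only). A patient can therefore lose doses to the toxicity under study, have no DLT, and leave the count.

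Finding the recommended dose is the Phase Ib primary objective, and the DLT count is its formal input. In a cohort of about 4 patients, one unreported replacement changes what a result of 0 in 3 means. The plan does not ask for replacements, or their reasons, to be reported.

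**Working it through.** **1. Classification of toxicity-related palbociclib holds in C0/C1** (Sections 10.2.3 and 10.4.2, Table 6)

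| Hold in Cycle 1 | DLT? | Replaced? |
|---|---|---|
| Grade 3 neutropenia without fever, 5 or more doses | No neutropenia or interruption item applies | Yes |
| Grade 4 neutropenia without fever, under 10 days, 5 or more doses | No | Yes |
| Non-hematologic toxicity not otherwise a DLT, 5 to 7 days | No | Yes |
| Non-hematologic toxicity, more than 7 days | Yes | No |

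Example: Grade 4 neutropenia on Days 8 to 16 lasts 9 days and costs at least 9 doses. It is not a DLT, and the patient is replaced. GDC-0810 has a smaller gap: a hold of exactly 7 days, or 7 or more scattered missed doses.

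**2. How easily 5 doses are missed.** Palbociclib is given on Days 1–21, and Appendix 3 marks Cycle 1 hematology on Days 8, 15 and 22 (±1 day). A hold from Day 8 to the Day 15 count misses Days 8–14, which is 7 doses. From Day 15 to Day 22 it misses Days 15–21, again 7. With the windows the range is 5 (for example Day 9 to Day 14) to 9 (Day 7 to Day 16). A hold starting on Day 22 misses none. This assumes no unscheduled count. Grade 4 events have an extra early count, so the weekly arithmetic mainly describes Grade 3 holds.

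**3. Phase Ia and D1.** Any toxicity interruption beyond 7 days is a DLT there. With once-daily dosing the gap is only about 7 missed doses.

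**4. Table 11 reproduced.** P(escalate) = (1−p)³ + 3p(1−p)²·(1−p)³. At p = 10%: 0.729 + 0.243 × 0.729 = 90.6% (stated 91%). All ten entries reproduce. The formula has no term for replacement.

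**5. Adding replacement.** Let p be the DLT probability and r the probability of a non-DLT toxicity hold that triggers replacement. The documents do not give r; 10–50% is an assumption. The DLT rate among evaluable patients is p/(1−r). For p = 10%:

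| r | p/(1−r) | P(escalate): replaced | kept as non-DLT | counted as DLT (p+r) |
|---|---|---|---|---|
| 10% | 11.1% | 88.7% | 90.6% | 70.9% |
| 30% | 14.3% | 82.8% | 90.6% | 30.9% |
| 50% | 20.0% | 70.9% | 90.6% | 8.2% |

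Under the protocol's own definition, replacement raises the observed DLT fraction and makes escalation less likely.

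**6. When replacement understates.** Let π be the DLT risk that held patients would have had under full dosing. The full-dosing rate is p + rπ, which exceeds p/(1−r) only if π > p/(1−r). With p = 10% and r = 30%, the evaluable rate is 14.3%. At π = 30% the full-dosing rate is 10% + 30% × 30% = 19%; at π = 50% it is 25%. P(escalate) at those rates is 73.0% and 60.0%, against 82.8%. The trial cannot observe π.

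**7. Frequency and weight.** P(at least 1 of the first 3 replaced) = 1−(1−r)³, which is 27%, 49%, 66% and 88% for r = 10%, 20%, 30% and 50%. Expected enrollment per 3 evaluable is 3/(1−r) = 3.3, 3.8, 4.3 and 6.0. One replaced patient behind a reported 0/3 gives 0/4 under the protocol definition, or 1/4 (25%) as an upper bound.

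**The case against.** **The definition is deliberate.** The C0/C1 list is stated to reflect known and expected toxicities, and brief neutropenia is expected with palbociclib. Counting such a hold as a DLT would override that choice. This stands, so that count serves only as an upper bound.

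**The hold is not clearly compulsory.** A reader might infer that the protocol forces a neutropenia hold in the DLT window and then discards the patient. Section 10.4.2 says only that interruptions may be used in the window. It introduces Table 6 as guidelines in the paragraph on the period after the window, and its list of compulsory holds does not include neutropenia. Table 6 supports such a hold; the documents do not support calling it mandatory in the window.

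**Hidden toxicity is not shown.** A reader might infer that replacement makes the combination look safer than it is. Steps 5 and 6 show that this needs a further assumption about held patients.

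**The frequency is unknown.** Section 2.2 cites Grade 3 and Grade 4 neutropenia of 48% and 6% with letrozole, and Grade 3 or higher of 65% with fulvestrant. These are whole-study incidences from other trials, not Cycle 1 rates of holds costing 5 doses, so they cannot be used as r. Section 11.2 also allows extra local tests, which could shorten holds.

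**Other safeguards exist.** Adverse event, laboratory and dosing data are reviewed before escalation, and C1 can be de-escalated without DLTs (Section 10.1.3.1). Replaced patients stay in the safety population, with dose modifications flagged (Section 15.3). These mitigate, but they do not show who left the DLT denominator or why.

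**Enrollment is closed.** Section 1.1 reports 4 patients in C1, each treated for at least 56 days, and no neutropenia among related events above 20%. That is weak reassurance: the data are preliminary, and the protocol defines study drug as GDC-0810, so palbociclib-related neutropenia may not be listed. The objection does limit the remedy to clarification and reporting.

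**Conclusion.** The misalignment in C0/C1 stands on the text. Some treatment-related palbociclib holds are not DLTs yet cause replacement, so the evaluable set is chosen partly by a treatment-related outcome that Table 11 does not model. The Phase Ia gap is narrow and should not be given equal weight.

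The documents do not establish an understated DLT rate. Under the stated definition the observed fraction moves up, from p to p/(1−r); understatement requires held patients' latent risk to exceed p/(1−r). Every size given for r rests on the assumed 10–50% range, and the documents do not say whether any patient was replaced. The firm consequence is that a DLT rate in a cohort of about 4 cannot be interpreted without knowing who was replaced and why.

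**What to change.** Reconcile Sections 10.2.1, 10.2.3 (including the C0/C1 DLT definitions), 10.4.2 and Table 6 on how missed doses caused by treatment toxicity are classified for the DLT count. This needs a consistent classification only; no hold or dose rule is proposed here.

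For each completed dose-finding cohort, report patients enrolled, DLT-evaluable and replaced, with the reason and doses missed for each replacement. Give the DLT rate as defined. As a sensitivity analysis, repeat it with toxicity-related replacements kept in, first as non-DLT (the protocol definition) and then as DLT (upper bound only, labelled as such).

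The cost is a wording change and one small table from dosing and adverse event data already collected. The upper-bound rate may look less favourable, particularly in a cohort this small.
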